3.2. Secondary Endpoint(s)

The secondary endpoints are listed below will consider a participant as diagnosed with ATTR-CM based on the definition in [Section 6.1.1.1](#).

- Estimate of prevalence of ATTR-CM in participants with HFpEF within the following subgroups, where prevalence within each subgroup is defined as the number of participants meeting the diagnosis criteria in [Section 6.1.1.1](#) divided by the number of evaluable participants in the study in the given subgroup category:
 - Regions (North America, Europe, Asia);
 - Age categories (60-64, 65-69, 70-74, 75-79, 80-85, >85);
 - Gender (male, female).
- Participants diagnosed with ATTR-CM will be evaluated for TTR genotype, ie, wild-type or hereditary form. The proportions of these two genotypes will be evaluated as a secondary endpoint
- Baseline characteristics of HFpEF participants with and without ATTR-CM:
 - NYHA classification: Participants will be evaluated using the New York Heart Association classification at baseline visit (day 1). Detailed description of each class (Class I, Class II, Class III, Class IV) is available in Section 8.2.12 of the protocol.
 - NT-proBNP: A biomarker that will be assessed during visit 1.

CCI

CCI

CCI

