4.2. Scientific Rationale for Study Design

It has recently been described that ATTR amyloidosis is significantly underdiagnosed, taking into consideration that both the clinical presentation and the symptoms are non-specific. The most frequent form of HF in patients with ATTR-CM is HF with preserved left ventricular ejection fraction (HFpEF). The aim of this epidemiology study is to assess the prevalence of ATTR-CM in a clinically at risk HFpEF population. Inclusion of an age criteria of ≥ 60 years enables only at-risk HFpEF participants to be enrolled.

Definitive diagnosis of ATTR-CM may include invasive tissue biopsy. Extracardiac biopsy has a low diagnosis yield in ATTR amyloidosis, particularly in wild-type ATTR (ATTRwt). Therefore, in the setting of high clinical suspicion and a negative extracardiac biopsy, endomyocardial biopsy would be required. This invasive diagnostic approach carries

associated complications and delays in diagnosis.²² Alternatively, noninvasive cardiac scintigraphy has marked a crucial change in the diagnostic workup of the disease. Data show that a Grade 2 or 3 uptake, in the absence of monoclonal proteins on serum and urine immunofixation electrophoresis and serum free light chain assay, is associated with 100% sensitivity and 100% specificity for cardiac ATTR amyloidosis.²² In the case of Grade 1 uptake, histological confirmation through endomyocardial biopsy with typing of amyloid is required.

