6. ANALYSES AND SUMMARIES

6.1. Primary Endpoint(s)

The primary endpoint is an estimate of the global prevalence of ATTR-CM in HFpEF participants. Diagnosis of ATTR-CM is defined as:

- Cardiac Scintigraphy Grade 1, with confirmation of ATTR by cardiac biopsy during the study period, or:
- Cardiac Scintigraphy Grade 2 or above.

The primary endpoint will be evaluated by dividing the number of participants who are classified as ATTR-CM positive by Cardiac Scintigraphy (as noted above) by the total number of HFpEF evaluable participants in the study. The proportion of Scintigraphy Grade 1 participants that are diagnosed with ATTR-CM will be estimated. Scintigraphy

Grade 1 participants that are diagnosed with ATTR-CM using a criteria other than cardiac biopsy and participants lost to follow-up without a confirmation of cardiac biopsy will be assumed as not diagnosed with ATTR-CM in the primary analysis. Exact 95% confidence intervals for the prevalence will be calculated using the method of Clopper and Pearson.¹ The primary analysis will be generated using the “Evaluable Analysis Set”.

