6.1.1.1. Sensitivity/Supplementary Analysis

As a sensitivity analysis, the prevalence will be estimated using the diagnosis criteria described in the primary endpoint, but will include all participants with Scintigraphy Grade 1 diagnosed with ATTR-CM in the study (regardless of the cardiac biopsy). Specifically, participants with Scintigraphy Grade 1 that were diagnosed with ATTR-CM using a criteria other than cardiac biopsy will be included in the estimate of prevalence in this sensitivity analysis. Scintigraphy Grade 1 participants that are lost to follow-up prior to a diagnosis of ATTR-CM will be assumed as not diagnosed with ATTR-CM. The proportion of Scintigraphy Grade 1 participants that are diagnosed with ATTR-CM will be estimated.

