9. APPENDICES

Appendix 1. Summary of Primary, Secondary, CCI ██████████ Analyses

Endpoint	Analysis Set	ATTR-CM vs HFpEF Participants	Analysis of ATTR-CM Participants by		Analysis
			Scintigraphy Grade	NYHA Baseline Classification	
Primary					
Global prevalence of ATTR-CM among participants with HFpEF.	Evaluable	N/A	N/A	N/A	Prevalence
Sensitivity/Supplementary Analysis					
Global prevalence of ATTR-CM as defined in Section 6.1.1.1 among participants with HFpEF will be estimated using the diagnosis criteria described in the primary endpoint, but will include all participants with Scintigraphy Grade 1 diagnosed with ATTR CM in the study (regardless of the cardiac biopsy).	Evaluable	N/A	N/A	N/A	Prevalence
Prevalence of ATTR-CM as defined in Section 6.1.1.1 among participants with HFpEF (regardless of the cardiac biopsy) in sub-groups (regions, age categories, gender).	Evaluable	N/A	N/A	N/A	Prevalence
Secondary					
Prevalence of ATTR-CM as defined in Section 6.1.1.1 among participants with HFpEF in sub-groups (regions, age categories, gender).	Evaluable	N/A	N/A	N/A	Prevalence
Proportion of participants with WT and hereditary forms among participants diagnosed with ATTR-CM as defined in Section 6.1.1.1 .	All Enrolled	✓	✓	✓	Proportion

New York Heart Association (NYHA) classification.	All Enrolled	✓	✓	N/A	Proportion
NTproBNP.	All Enrolled	✓	✓	✓	Descriptive Mean

CCI

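### Region, age and gender prevalence is planned only under the SAP 6.1.1.1 case definition, so it cannot be set against the primary global estimate once any Grade 1 participant is diagnosed without cardiac biopsy

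*SAP*

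**What the plan says.** The Protocol (1.1, 3 and 9) has one case definition: scintigraphy Grade 2 or above, or Grade 1 confirmed by cardiac biopsy. Its rationale in 4.2 adds: "In the case of Grade 1 uptake, histological confirmation through endomyocardial biopsy with typing of amyloid is required".

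SAP 6.1 keeps that definition for the global primary estimate, with the Grade 1 arm worded as "Cardiac Scintigraphy Grade 1, with confirmation of ATTR by cardiac biopsy during the study period, or". It then names two groups, "Grade 1 participants that are diagnosed with ATTR-CM using a criteria other than cardiac biopsy and participants lost to follow-up" without biopsy confirmation, and treats both as not having ATTR-CM.

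SAP 6.1.1.1 sets a wider definition as a sensitivity analysis. It "will include all participants with Scintigraphy Grade 1 diagnosed with ATTR-CM in the study (regardless of the cardiac biopsy"), and it specifies that "participants with Scintigraphy Grade 1 that were diagnosed with ATTR-CM using a criteria other than cardiac biopsy will be included in the estimate of prevalence".

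SAP 3.2 assigns that wider definition to every secondary endpoint: "The secondary endpoints are listed below will consider a participant as diagnosed with ATTR-CM based on the definition in" Section 6.1.1.1. SAP 2.1, 5.2.1 and 6.2 say the same. In Appendix 1, one row under the sensitivity heading reads "Prevalence of ATTR-CM as defined in Section 6.1.1.1 among participants with HFpEF (regardless of the cardiac biopsy) in sub-groups (regions, age categories, gender"). The first row under the secondary heading describes the same estimate, by the same definition, on the same analysis set.

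**The concern.** The secondary objective is variation in prevalence at country, regional and global level. A reader will naturally put the regional figures beside the headline global figure. As planned, a Grade 1 participant diagnosed by a non-biopsy method is a non-case in the headline and a case in the regional, age and gender tables. The denominator is the same, so the whole discrepancy sits in the numerator, and no planned output lets the reader remove it subgroup by subgroup.

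The participants who move between definitions are also those whose work-up the study does not control. Under Protocol 8.2.1, confirmatory test data are collected only where testing is done. Protocol 8.1.4 and 8.2.18 record whichever method was used, and the visible text lists no accepted non-biopsy criteria. Part of any regional difference could therefore reflect how Grade 1 scans are followed up locally.

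**Working it through.** **Inputs from the documents.** N = 2000, anticipated prevalence 10%, 200 expected cases, stated precision ±2.5% (Protocol 9); exact Clopper-Pearson 95% intervals (SAP 5.2.1); Evaluable Analysis Set for primary, sensitivity and secondary prevalence (SAP 4).

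**Inputs assumed.** The documents give neither the share of participants with Grade 1 (g) nor the share of those diagnosed without biopsy (d). I use g = 1% to 10% and d = 10% to 50%, with d = 0 as the boundary case.

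**Step 1: the plan's own figures.** Expected cases: 2000 × 0.10 = 200, as stated. Normal-approximation half-width: 1.96 × √(0.10 × 0.90 / 2000) = 1.32 points. The exact interval for 200/2000 is 8.72% to 11.40%, a half-width of (11.40 − 8.72)/2 = 1.34 points. The stated ±2.5% is not reproduced. It is looser than the design achieves, since n = 554 would be enough for it, and nothing below depends on it.

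**Step 2: the definitions side by side.**

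| Participant | Primary (SAP 6.1) | Subgroups (SAP 6.1.1.1) |
|---|---|---|
| Grade 2 or 3 | case | case |
| Grade 1, biopsy confirms ATTR | case | case |
| Grade 1, diagnosed by another method, no biopsy | not a case | case |
| Grade 1, lost to follow-up without diagnosis | not a case | not a case |
| Grade 1, biopsy negative, diagnosed by another method | not a case | not stated |

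Apart from the last row, where the text is silent, the 6.1.1.1 cases are the primary cases plus the third row. Hence:

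gap = 6.1.1.1 prevalence − primary prevalence = g × d.

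**Step 3: size of the gap.** Take 200 primary cases in 2000. Extra cases = 2000 × g × d, and the implied overall prevalence is (200 + extra)/2000. Each cell gives extra cases, then prevalence.

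| g | d = 10% | d = 25% | d = 50% |
|---|---|---|---|
| 1% | 2, 10.1% | 5, 10.25% | 10, 10.5% |
| 3% | 6, 10.3% | 15, 10.75% | 30, 11.5% |
| 5% | 10, 10.5% | 25, 11.25% | 50, 12.5% |
| 10% | 20, 11.0% | 50, 12.5% | 100, 15.0% |

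The gap runs from 0.1 to 5.0 points and is zero when d = 0. It first exceeds the 1.34-point half-width in this grid at g = 3%, d = 50% (1.5 points). The half-width is only a yardstick: the gap is a reclassification of the same people, not sampling error.

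**Step 4: dependence on local practice, both ways.** Take two regions with identical uptake: 10% Grade 2 or 3, and 5% Grade 1.

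- No biopsies in either region. Region A diagnoses no Grade 1 participants by other means and Region B diagnoses half. Under 6.1.1.1: A 10.0%, B 10.0 + 5 × 0.5 = 12.5%. Under the primary definition: both 10.0%.
- No diagnoses by other methods. In A no Grade 1 participant is biopsied; in B half are biopsy-confirmed. Under the primary definition: A 10.0%, B 12.5%. Under 6.1.1.1: the same, because biopsy-confirmed cases count there too.

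Each route can produce the same 2.5-point difference, so which definition distorts regional comparison more cannot be settled from the documents.

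**The case against.** The strongest reply is that this is a declared choice. SAP section 1 (Tables 1 and 3) records the move of the secondary and safety analyses to 6.1.1.1. SAP section 2 allows the SAP to modify protocol plans and calls for a protocol amendment only for major changes to the primary endpoint or its analysis, which is untouched here. A reader might infer an undisclosed departure from the Protocol; the documents do not support that.

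Second, the subgroup figures are not orphaned. Global prevalence under 6.1.1.1 is reported on the same Evaluable set, and the subgroup numerators sum to it, apart from subgroups under 50, which SAP 6.2 does not estimate. The proportion of Grade 1 participants diagnosed is also reported, so the overall gap can be seen. This stands, but it does not give the gap by region, age or gender.

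Third, a reader might infer that the primary definition would make the regional comparison safe and should simply replace 6.1.1.1. Step 4 shows otherwise: biopsy is not a study procedure and Grade 1 without biopsy confirmation counts as negative, so subgroup prevalence under the primary definition would track local biopsy rates. Replacement would also leave genotype, NYHA, NT-proBNP and safety tables on different case counts from the subgroup prevalence tables. This stands in full and is why both versions are needed.

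Fourth, it is tempting to read the phrase about disregarding biopsy in 6.1.1.1 as counting biopsy-negative participants. The sentence after it narrows the meaning to diagnoses made by another criterion. The text does not exclude a biopsy-negative case, but nothing shows that one was intended.

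**Conclusion.** The point holds as a problem of comparability and presentation. The SAP plans region, age and gender prevalence under 6.1.1.1 only, while the headline global figure uses the biopsy-confirmed definition. The two will not reconcile if at least one Grade 1 participant is diagnosed without biopsy; otherwise the gap is nil. A reader might conclude that the subgroup totals must exceed the primary, or by a known amount. Neither follows: the range of 0.1 to 5.0 points rests wholly on the assumed Grade 1 share (1% to 10%) and non-biopsy diagnosis share (10% to 50%). The lower part of that range is small beside the primary half-width of about 1.3 points; the upper part is well above it. The primary estimate itself is not affected.

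Both definitions carry local work-up into the regional comparison, through biopsy rates in one and unlisted non-biopsy criteria in the other. Showing both, with the Grade 1 work-up behind them, is the only way the planned data can reveal how much of a regional difference comes from practice.

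**What to change.** 1. In Appendix 1, use one of the two identical subgroup rows for region, age and gender prevalence under the primary definition, and keep the other for the 6.1.1.1 version. Carry this into SAP 2.1, 3.2, 5.2.1 and 6.2.
2. Present the two versions side by side, each labelled with its definition and set against its matching global estimate: the primary with the primary, 6.1.1.1 with the sensitivity estimate.
3. Tabulate by region the number of Grade 1 participants, the number biopsied and the result, and the number diagnosed by each other method.
4. State in 6.1.1.1 how a Grade 1 participant whose cardiac biopsy was negative for ATTR is classified.
5. Leave the genotype, NYHA, NT-proBNP and safety tables on 6.1.1.1, and label their case counts with that definition.

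The cost is one extra table and some SAP wording. No new data are needed: Protocol 8.1.4 and 8.2.1 already provide for recording the method and result of Grade 1 follow-up testing where it is done.

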3.4. Baseline Variables

This study does not have a study treatment and all assessment for the primary, secondary, and CCI endpoints, are collected either during the Screening Visit or Visit 1 (Day 1).

CCI

3.5. Safety Endpoints

Adverse events will be captured at screening, on day 1 and through the follow-up Visit 1. As there is no study treatment administered as part of this protocol, a definition of treatment emergence is not defined for adverse events. All adverse events documented in the study database will be reported and summarized.

4. ANALYSIS SETS (POPULATIONS FOR ANALYSIS)

All primary, sensitivity, and secondary endpoints estimating prevalence will be based on “Evaluable Analysis Set” defined below. All other endpoints, including CCI and safety endpoints will be evaluated using “All Enrolled Analysis Set”.

Population	Description
All Enrolled Analysis Set	All participants who meet the inclusion/exclusion criteria and completed Visit 1
Evaluable Analysis Set	All participants who meet the inclusion/exclusion criteria and completed Visit 1, excluding participants with Cardiac Scintigraphy assessed as non-evaluable

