8.3. Safety

8.3.1. Adverse Events

An AE is any untoward medical occurrence in a patient or clinical study participant, temporally associated with the use of study intervention, whether or not considered related to the study intervention.

NOTE: An AE can therefore be any unfavorable and unintended sign (including an abnormal laboratory finding), symptom, or disease (new or exacerbated) temporally associated with the use of study intervention.

Any AE that occurs from the time the participant provides informed consent through and including up to 14 days following the participant's last visit must be recorded. The investigator is required to assess whether the AE may be related to the participant's participation in the study. All AEs (i.e., serious and non-serious, including those attributed to qualifying procedure identified as research-related injury) are collected in the clinical study database.

The investigator must pursue and obtain information adequate to determine the outcome of the AE and to assess whether it meets the criteria for classification as a research related injury requiring immediate notification to Pfizer as described below.

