6.4. Safety Summaries and Analyses

6.4.1. Adverse Events

All adverse events and serious adverse events collected at the Screening Visit, Visit 1 or during follow-up, will be coded according to the Medical Dictionary for Regulatory Activities (MedDRA) and will be summarized by system organ class and preferred terms overall and separately for HFpEF participants diagnosed with ATTR-CM and HFpEF participants not diagnosed with ATTR-CM as defined in [Section 6.1.1.1](#). Participants with non-evaluable scintigraphy grade will be summarized in a separate group. All adverse events will be listed.

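### The SAP assigns safety endpoints to participants who were eligible and completed Visit 1, which conflicts with its promise to summarise all AEs and can leave procedure-related events out of the tables

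*SAP*

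**What the plan says.** SAP 4 defines two analysis sets and no separate safety set. The prevalence endpoints use the Evaluable Analysis Set. For the rest it says: "All other endpoints, including CCI and safety endpoints will be evaluated using" the All Enrolled Analysis Set (the letters in the middle mark a redaction). That set is "All participants who meet the inclusion/exclusion criteria and completed Visit 1", so a participant must satisfy both conditions.

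The safety sections of the SAP describe a wider scope. SAP 3.5 states "Adverse events will be captured at screening, on day 1 and through the follow-up Visit 1", and then "All adverse events documented in the study database will be reported and summarized". SAP 6.4.1 covers "All adverse events and serious adverse events collected at the Screening Visit, Visit 1 or during follow-up", to be tabulated by system organ class and preferred term, overall and by diagnosis group, with a further group for non-evaluable scans. It adds "All adverse events will be listed". It names no analysis set that would override SAP 4.

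Protocol 8.3.1 requires recording of "Any AE that occurs from the time the participant provides informed consent", and holds all AEs in the clinical study database. Protocol 9 (Safety Analysis) is narrower than the SAP on timing: it summarises AEs and research-related injuries from Visit 1 and follow-up. It sets no condition that Visit 1 be completed.

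**The concern.** In this study Visit 1 is the exposure. Protocol 6.2 defines the study intervention as the scan and the biological samples, and Protocol 8.1.2 places both at Visit 1. A safety set that requires the visit to have been completed therefore selects on something that can happen after the harm. If an AE stops the visit, the event and the person may leave the table together. Protocol 8.1 foresees that a safety issue may raise the question of whether a participant should continue.

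What is at stake is whether the AE tables describe everyone who underwent study procedures, and whether a programmer can carry out the SAP as written.

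**Working it through.** The plan gives no figure to reproduce. The check compares who is in the set with whose AEs are recorded and promised a summary.

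**Inputs.** Set membership: SAP 4. AE capture: from consent (Protocol 8.3.1) and from Screening (SAP 3.5). Promised summaries: SAP 3.5 and 6.4.1. Timing: Screening falls 3 to 28 days before Visit 1 (Protocol 1.4). Screen failures: the minimum record includes any SAE (Protocol 5.5).

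**Applying the SAP 4 rule to each group with recorded AEs**

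| Group | Visit 1 procedure started? | In All Enrolled set? | Summary promised by SAP 3.5 and 6.4.1? |
|---|---|---|---|
| Eligible, completed Visit 1 | Yes | Yes | Yes |
| (a) Screen failures | No | No | Yes |
| (b) Eligible, withdrew or died before Visit 1 | No | No | Yes |
| (c) Started Visit 1, did not complete it | Yes | No, on the plain reading | Yes |
| (d) Scanned, later found ineligible | Yes | No | Yes |

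The last two columns disagree in four of the five rows, so the two rules conflict. For groups (c) and (d), Protocol 9 promises a summary as well.

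**Direction of the effect on a procedure-related rate.** Leave group (d) aside. Let n participants start a Visit 1 procedure and m of them not complete the visit. Let x completers and y non-completers have a procedure-related event.

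- Rate among all who started: (x + y)/n.
- Rate in the All Enrolled set: x/(n − m).
- The second is lower when xn < (x + y)(n − m). This simplifies to xm < y(n − m), that is, y/m > x/(n − m).

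The reported rate is therefore too low whenever non-completers have procedural events more often than completers. That is to be expected if AEs are a reason for stopping.

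**The other groups do not fit this mechanism.** In (d), exclusion depends on eligibility and not on the event, so these people are omitted with no predictable direction. In (a) and (b) no Visit 1 procedure took place, so leaving them out hides no scan or sampling event. Adding them to the denominator would lower the procedural rate.

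**Size.** The documents give no screen-failure rate, no Visit 1 non-completion rate and no AE rate. None of n, m, x and y can be filled in.

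**A further gap.** The groups in SAP 6.4.1 are diagnosed, not diagnosed and non-evaluable scan. A participant who had no scan fits none of them and could appear only in the overall column.

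**The case against.** The strongest reply is that SAP 3.5 and 6.4.1 are the specific safety sections and SAP 4 is a general assignment, so the specific text should govern and nothing would be lost. That is a possible reading. But SAP 4 names safety endpoints expressly, and neither document says which rule prevails, so the conflict remains.

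A second reply is that neither document defines completion of Visit 1. A sponsor could count a partly performed visit as completed, and group (c) would then stay in. This stands as a limit: the exclusion of group (c) rests on the plain meaning of the words. It is also a reason to define the term.

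Third, all AEs will be listed, and medically important research-related injuries go to the sponsor at once (Protocol 8.3.2). Events are therefore not hidden. A listing has no denominator, however, and is not the summary that SAP 3.5 and 6.4.1 promise.

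Fourth, group (d) should be small. Protocol 5 and 8.1 bar waivers and require eligibility to be confirmed from the screening evaluations, so a scanned ineligible participant would be a deviation. That is fair, but such a person still had the procedure.

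Two stronger readings are tempting. A reader might size the problem by assuming a percentage of consented participants who never complete Visit 1. Such a count would include screen failures and early withdrawals who were never scanned, so it does not measure lost procedural events. A reader might also infer that the reported AE rate changes materially. The documents contain no AE or non-completion rate that would support this.

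**Conclusion.** The concern holds as an internal conflict in the SAP with a specific consequence. SAP 4 cannot be reconciled with SAP 3.5 and 6.4.1 as written. If SAP 4 governs and completion has its ordinary meaning, participants who start but do not complete Visit 1, and those scanned and later found ineligible, are missing from the AE tables.

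Downward bias in procedure-related AE rates can be argued only for the first group, and only if their event rate exceeds that of completers. Its amount cannot be estimated from the documents.

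The weight is moderate. No study treatment is given, the safety analysis is descriptive, and the prevalence estimates use a different set and do not change. The point should still be settled before the AE tables are programmed, because the affected group is the one in whom a procedural problem is most likely to show.

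**What to change.** 1. Add a Safety Analysis Set to SAP 4: all participants in whom any Visit 1 procedure was started, whether or not the visit was completed and whether or not they were later found ineligible. Move the safety endpoints from the All Enrolled Analysis Set to this set.
2. Use it for the AE summaries in SAP 6.4.1, with a separate column for participants without a scintigraphy grade alongside the existing group for non-evaluable scans.
3. Summarise AEs between consent and Visit 1 separately, for all consented participants and including SAEs in screen failures. This meets SAP 3.5 and 6.4.1 without diluting the procedural denominator. Footnote that the minimum screen-failure record in Protocol 5.5 assures only SAEs, so non-serious events in that group may be incomplete.
4. Define completion of Visit 1, since the All Enrolled and Evaluable sets both depend on it.

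The cost is one set definition and one extra table or column. AEs are already recorded from consent under Protocol 8.3.1, apart from the caveat in item 3. The sponsor should confirm that the case report form shows which Visit 1 procedures were started. Restricting SAP 3.5 and 6.4.1 to the All Enrolled Analysis Set would also remove the contradiction, but it would keep the exclusion of participants whose visit was cut short.
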